3.2. Rationale Number of Subject

A sample size of 90 subjects will be determined with difference 0 g/dL, standard deviation 0.8 g/dL, statistical power 90%, randomization ratio 1:1 to demonstrate equivalence at 5% significance level and equivalence margin ± 0.5 g/dL. Assumption of difference and standard deviation for sample size estimation in this study was derived from PDA10 ITT set. Difference between treatment groups in PDA10 ITT set was -0.009, but this study assumed to be 0. Standard deviation 0.8 was an approximate estimation derived from two-sided 90% confidence interval [-0.189, 0.171]. After an assumption of 10% drop-out rate for this trial, about 100 subjects will be enrolled to the trial. The sample size calculated using the POWER procedure (Proc Power procedure) of SAS ver. 9.4 (SAS Institute, Cary, NC, USA).

```

*****
+ PROGRAM NAME. : SAS Proc Power_EPO.sas
+ OUTPUT : EPO_Biosimilar_Sample Size_20191014.pdf
+ SAS VERSION : SAS 9.4
+ FIRST DATE : 14 Oct 2019
+ WRITTEN BY : DW Randomization Statistician
+ COMMENTS : Sample Size Calculation & Power for EPO_Biosimilar
+ : Reference: PDA10 Study
*****

proc power;
  twosamplemeans test=equiv_add
  lower = -0.5
  upper = 0.5
  meandiff = 0
  stddev = 0.8
  groupweights = (1 1)
  ntotal = .
  power = 0.9;
run;

```

Figure 4. SAS code used in determining study subject number

Figure 5. SAS output

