3.2 Number of Research Subjects and Estimated Number of Samples

3.2.1. Number of Subjects

The total number of subjects in this study is 100 subjects. Only subject who achieve baseline target Hb level 10-12 g/dL will continue to maintenance period. Subject will be randomized into 2 study arms. For the randomized allocation code between reference product (Eprex®) and test product (Epodion®) will be maintained ratio 1:1.

Study Group	Epodion®	Eprex®
Evaluated	50 Subjects	50 Subjects

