7.4.1 Primary Endpoint

Change in Hb levels from baseline to the evaluation period

Descriptive statistics will be provided by treatment group. The difference between treatment groups will be determined by ANCOVA (analysis of covariance) model with treatment as factor, and baseline Hb level and the change in weekly dosage per kg body weight from baseline to the evaluation period of Epodion® or Eprex® as covariates.

Therapeutic equivalence of Epodion® to the comparator Eprex® will be demonstrated if the two-sided 90% confidence interval of the difference of mean changes in Hb levels between treatment groups lay within the interval of ± 0.5 g/dL.

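### The protocol's own inputs require 114 evaluable subjects for 90% power; the stated 90 give about 80%

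*Protocol*

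**What the plan says.** Protocol section 3.2 (rationale for the number of subjects) gives the size and its inputs: "A sample size of 90 subjects will be determined with difference 0 g/dL, standard deviation 0.8 g/dL, statistical power 90%, randomization ratio 1:1", the purpose being "to demonstrate equivalence at 5% significance level and equivalence margin ± 0.5 g/dL". The zero difference is a choice: "Difference between treatment groups in PDA10 ITT set was -0.009, but this study assumed to be 0". The SD of 0.8 g/dL is said to be approximated from the 90% confidence interval of that same earlier study. The printed PROC POWER code uses `test=equiv_add` with limits -0.5 and 0.5, mean difference 0, SD 0.8, equal group weights and power 0.9, and it solves for the total N. The dropout step follows: "After an assumption of 10% drop-out rate for this trial, about 100 subjects will be enrolled to the trial".

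The decision rule in protocol section 7.4.1, repeated in SAP section 3.1, is that equivalence is shown if the "two-sided 90% confidence interval of the difference of mean changes in Hb levels between treatment groups lay within the interval of ± 0.5 g/dL".

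Section 3.2.1 says "The total number of subjects in this study is 100 subjects". Its table, like the synopsis, labels the 50 + 50 as evaluated.

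**The concern.** Equivalence requires both confidence limits to fall inside the margin. When the true difference is zero, the chance of failing is split equally between the two limits. A size that gives 90% power against one limit therefore gives only about 80% against both, and 90 looked too small for a two-limit test with these inputs.

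The equivalence test on Hb change is the trial's only formal efficacy claim, and the 90% figure is its design justification. If that figure is wrong, anyone who approves the trial on the strength of the protocol is told that the risk of an inconclusive result is half what it is. A failed result would later be judged against a power the design never had.

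**Working it through.** **Inputs, all from protocol sections 3.2 and 7.4.1**

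- margin m = 0.5 g/dL on each side
- SD σ = 0.8 g/dL
- true difference 0
- 1:1 allocation
- α = 0.05 per side. The printed code sets no alpha; this value follows from the stated 5% level and the 90% interval rule.
- target power 90%
- dropout 10%

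**Step 1: the plan's own figures.** The dropout step reproduces: 90 / (1 - 0.10) = 100. The 90 itself does not reproduce from the stated test and power, as follows.

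**Step 2: normal approximation.** For equivalence at zero difference, the size per arm is

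n = 2σ²(z₀.₉₅ + z₁₋β/₂)² / m²

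With β = 0.10, z₁₋β/₂ = z₀.₉₅ = 1.645, so

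n = 2 × 0.64 × (1.645 + 1.645)² / 0.25 = 55.4, rounded up to 56 per arm, 112 in total.

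In the other direction, at N = 90:

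- SE = 0.8 × √(4/90) = 0.1687
- power = 2Φ(0.5/0.1687 - 1.645) - 1 = 2Φ(1.32) - 1 = 81.3%

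**Step 3: exact calculation.** This is the power of two one-sided pooled t tests at 5% each with N - 2 degrees of freedom, integrating over the sampling distribution of the pooled variance.

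| Total evaluable N | Exact power | Risk of missing equivalence |
|---|---|---|
| 88 | 79.4% | 20.6% |
| 90 | 80.5% | 19.5% |
| 100 | 85.5% | 14.5% |
| 112 | 89.9% | 10.1% |
| 114 | 90.5% | 9.5% |

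The smallest even total for 90% power is 114 (57 per arm). The smallest for 80% is 90. A simulation with 1,000,000 replicates gave 80.6% at N = 90 and 90.6% at N = 114.

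**Step 4: does any other reading give 90?**

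- Stricter level, 2.5% per side: 136 subjects for 90% power.
- True difference -0.009 instead of 0: still 80.5% at N = 90.
- Two-sided 5% superiority test for a difference of 0.5: 108 subjects.
- Same equivalence test with 80% power: exactly 90 subjects.
- Single one-sided 5% t test against one margin, 90% power: exactly 90 subjects (power 90.3%). The normal version is 2 × 0.64 × (1.645 + 1.282)² / 0.25 = 43.9, so 44 per arm, 88 in total.

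Only the last two return 90. One does not have the stated power; the other is neither the coded test nor the decision rule. The documents do not show which of them, if either, produced the figure.

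**Step 5: SD needed for 90% power.** At N = 90 the SD would have to be about 0.715, and 1 - (0.715/0.8)² = 20% less variance. At N = 100 it would have to be about 0.755, and 1 - (0.755/0.8)² = 11% less variance.

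**Step 6: size after dropout.** 114 / 0.90 = 126.7, so 127 randomised, or 128 for equal arms.

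**The case against.** The strongest objection is that the primary analysis is an ANCOVA with two covariates, whereas these figures are for an unadjusted comparison. If the covariates explained about 20% of the variance, 90 subjects would reach 90% power; if all 100 were evaluable, about 11% would do. That is possible, but the protocol claims no such gain. It sizes on SD 0.8 with an unadjusted test, and nothing shows whether 0.8 already comes from an adjusted analysis. The objection softens the statement about actual power but does not make section 3.2 correct.

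The SAS output figure is not available to check. That does not change the conclusion, because the prose and the printed code give the same inputs and those inputs fix the answer.

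It is also fair to say that the trial could not produce a false equivalence claim more often because of this error. The interval rule is untouched, and the harm is a higher risk of an inconclusive result in a Phase IV study. That stands, and it is why resizing is optional.

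Finally, one might ask whether the 100 is counted before the Eprex run-in. If 10% to 30% failed the run-in (an assumption) and 10% of the rest dropped out, 81 down to 63 would be evaluable, with power of about 75% down to 58%. The documents point away from this reading: the footnotes to the synopsis schedule treat titration failures as screen failures, and the 100 is tabulated by arm. The conclusion does not rest on it.

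**Conclusion.** Section 3.2 is wrong as written: 90 subjects and 90% power cannot both stand. Under its own inputs, power at 90 evaluable subjects is 80.5%, which is 9.5 points below the claim. The required number is 114, which is 24 more. Even if all 100 were evaluable, power would be 85.5%.

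This rests on SD 0.8, true difference 0, margin ±0.5, 5% per side, equal arms and an unadjusted comparison. The SD itself cannot be verified, because the protocol does not give the size of the earlier study. The interval's half-width is (0.171 + 0.189)/2 = 0.18, so an SD of 0.8 would imply about 4 × (0.8 × 1.645/0.18)² = 214 subjects there.

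The evaluated-versus-enrolled wording is a separate, smaller inconsistency in the same sections.

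**What to change.** Correct protocol section 3.2 in one of two ways.

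1. **Keep the size and restate the power.** Say that 90 evaluable subjects give about 80% power, and 100 evaluable about 85%, with SD 0.8, true difference 0, margin ±0.5 g/dL and a two-sided 90% interval. Change the power value in the printed code to match. This costs wording only, though the stated power becomes less favourable.
2. **Keep 90% power and change the size.** State 114 evaluable subjects, and about 127 randomised at 10% dropout (128 for equal arms). This costs about 27 more randomised subjects than the planned 100.

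If the sponsor relies on a covariate gain to support 90, section 3.2 should state the residual SD assumed and its source.

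In either case, use one set of terms in the synopsis, section 3.2.1 and section 3.2. Under the arithmetic of section 3.2 this would be 100 randomised and 90 evaluable. Say explicitly that subjects who fail the run-in are not counted in the 100.

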3.4 Allocation of Treatment Group

To guarantee scientific appropriateness of the clinical study, investigator's subjective opinion shall not intervene in assignment of subjects into each treatment group, and randomization procedure will be used, based on the concrete probabilistic theory.

Randomization is done using envelopes. The envelope contains information about the product that the subject will receive. Once randomization envelope is opened, it cannot be re-issued to another subject. Randomized allocation code between reference product (Eprex®) and test product (Epodion®) will be maintained ratio 1:1.

CHAPTER 4. ASSESSMENT AND PROCEDURE OF STUDY

4.1 Efficacy Evaluation

4.1.1 Primary Endpoint

To demonstrate that the Epodion® treatment is equivalence to Eprex® by evaluating Hb level change between baseline (Week 5-8/9-12) and evaluation period (Week 33-36/37-40).

4.1.2 Secondary Endpoint

1. Obtain data mean change in weekly dosage per kg body weight between the baseline period and the evaluation period.
2. Calculating instability rate of Hb (hemoglobin) level during maintenance and evaluation period as defined when Hb (hemoglobin) level dropped below 8 g/dL or increase more than 13 g/dL.
3. Evaluating Hb (hemoglobin) and hematocrit level during maintenance and evaluation period.

4.2 Safety Evaluation

Safety was evaluated based on incidence of adverse event.

Reported any symptoms from subject or other health care practitioner defined adverse event if appear after subject administered with investigational product (both Eprex® or Epodion®), and divided into local reactions and general reactions, and the details are as mentioned below:

- a. Local reaction: Pain, Tenderness, Erythema/Redness, Induration/Swelling
- b. Systemic reaction: Fever, Nausea/vomiting, Diarrhea, Headache, Fatigue, Myalgia.

Vital sign abnormalities are defined as adverse event if there are any clinical significance increase or decrease value including blood pressure, body temperature, heart rate, and respiratory rate after subject administered with investigational product (both Eprex® or Epodion®).

Laboratory test findings defined as adverse event if there are any clinical significance increase or decrease laboratory results including hematology test, blood chemistry test, and urinalysis after subject administered with investigational product (both Eprex® or Epodion®). If any findings after subject administered with investigational product disease temporary, finding abnormalities of electrocardiogram, X-ray, MRI also recorded as adverse event.

4.3 Others

4.3.1 Demographic Investigation

Prior to participation in the clinical study, objective and content of this clinical study shall be explained to the subjects and LAR in detail, informed consent shall be obtained from them, screening number shall be given according to the sequence of receiving informed consent, and then demographic information shall be recorded. Records include written consent, date of consent, gender, date of birth, and age.

4.1.3 Investigation of medical and medication history

Medical history and medication history of the subject shall be investigated and recorded in detail by medical interview. Content that must be included in the medical history and medication history is as mentioned below.

For medical history, past history and current illness including surgical history, and hypersensitivity during 6 months before screening period shall be investigated. Time of onset (year or date of onset), investigator's opinion, etc. shall be written.

For medication history, medication history and current status of erythropoietin administration (dosage, dose, period, etc.) during the 4 weeks prior to screening period shall be investigated. Also, history of medication with cyclosporin and androgen during 3 months prior to screening period, shall be recorded.

If there is any change of concomitant medication compared to the medication investigated at screening, the information shall be documented in the CRF in detail.

4.4 Study Procedure

This research consists of a screening period (4 weeks), titration period (4~8 weeks) baseline evaluation period (4 weeks), maintenance period (24 weeks) and 4 weeks for evaluation period. For each subject, the end of the study was the last day of evaluation. In the case of a subject that has left the study (withdrawn), the exit date will be the end of the study.

Procedure and Assessment	Screening	Titration Period				Baseline Period				Maintenance Period																Evaluation Period			
										10/14	12/16	14/18	16/20	18/22	20/24	22/26	24/28	26/30	28/32	30/34	32/36	34/38	36/40						
Week	-4	0	2	4	6	8	10	12																					
Informed consent form	■																												
Patient demography	■																												
Medical history	■																												
Prior Medication	■																												
Inclusion/exclusion criteria	■																												
Baseline Target Evaluation ¹⁾					■	■	■	■																					
Randomization ³⁾						■	■	■																					
Concomitant Medication																													
Eprex® administration ²⁾																													
Epodion® administration ²⁾																													
Lab Test	CBC (Hb)	■	■	■	■	■	■	■	■	■	■	■	■	■	■	■	■	■	■	■	■	■	■	■	■	■	■	■	■
	CBC (Hct)	■																											
	Iron status	■					■																						
	HIV	■																											
	Blood Chemistry (ALT&AST)	■																											
Pregnancy Test	■																												
Safety Assessment ⁴⁾																													

Figure 6. Study method

[figure not shown]

Figure 7. Study flow

4.4.1 Subject screening (-4 weeks)

Patient eligibility was assessed before study begins based on screening criteria and before entering maintenance period based on inclusion and exclusion criteria of study as stated in the protocol. Once subjects voluntarily consented to participate in the clinical study, medical examinations and tests required in the protocol will be conducted, eligibility of each subject will be checked, and only subjects who meet all of the screening criteria will be proceeded for first phase of study which is titration period.

4.4.2 Titration Period (Week 0-4/0-8)

In the Titration period (4 ~ 8 weeks), all eligible subjects will be given Eprex® at individualized dose for 3 times a week through intravenous injection. In this period, the Hb level of the subject was controlled to reach the target range of 10-12 g / dL. Patient demographics, patient medical history, and routine hematological test will be obtained in this period.

4.4.3 Baseline Evaluation Period (Week 5-8/9-12)

Week 5-8/9-12 is the baseline evaluation period. Hemoglobin mean data and mean weekly Epoetin dose will be used as efficacy assessment parameter.

Before entering the maintenance period, subject inclusion and exclusion criteria are examined before subjects received a randomization number and were allocated into a test or control group.

4.4.4 Maintenance Period (Week 9-32/13-36)

During the maintenance period (Week 9-32/13-36), subjects who met the criteria were given Epoetin treatment according to the randomization allocation. Administration of Eprex® or Epodion® will be done with same doses regimen during titration period through intravenous injection. Epoetin dose may be increased or decreased at an appropriate level according to the condition of the subjects. Subject Hb levels were controlled to reach a range of 10-12 g/dL. Blood collection is carried out once every two weeks for the purposes of routine hematological test. Adverse event concomitant medication, and instability rate of Hb data is observed during the maintenance period. Concomitant medication during the study were recorded in the Case Report Form (CRF).

4.4.5 Treatment Evaluation Period (Week 33-36/37-40)

The week 33-36/37-40 is the treatment evaluation period. Hemoglobin mean data, weekly Epoetin dose, and hematocrit will be compared with the baseline period as an efficacy evaluation parameter. Adverse events, concomitant medication, and instability rate of Hb data is observed during the maintenance period.

4.4.6 Dose Information

Doses must be individualized to ensure that hemoglobin is maintained at an appropriate level for each subject. Screening period initials dose 50 IU/Kg body weight three times per week. During titration, titrated dose closely to achieve baseline Hb level 10-12g/dL. In maintenance period administer Eprex® and Epodion® equal previous stable dose in titration period. Dose is allowed to be increased or decreased during maintenance period at an appropriate level according to the condition of the subject.

CHAPTER 5. SELECTION OF SUBJECTS AND DROPOUT CRITERIA

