Randomization ³⁾																										
Concomitant Medication																										
Eprex® administration ²⁾									Administer at an appropriate level for each subject																	
Epodion® administration ²⁾									Administer according to the existing baseline dosage																	
Lab Test	CBC (Hb)	■	■	■	■	■	■	■	■	■	■	■	■	■	■	■	■	■	■	■	■	■	■	■	■	
	CBC (Hct)	■							■	■	■	■	■	■	■	■	■	■	■	■	■	■	■	■	■	
	Iron status	■							■	■	■	■	■	■	■	■	■	■	■	■	■	■	■	■	■	
	HIV	■																								
Blood Chemistry (ALT&AST)		■																								
		■																								
Pregnancy Test	■																									
Safety Assessment ⁴⁾									Every time																	

1. Subject must achieve baseline target Hb level 10-12 g/dL prior enter maintenance period. If during 4-week titration period subject did not achieve baseline Hb level 10-12 g/dL, titration period will be extended maximum until week 8.
2. Doses must be individualized to ensure that hemoglobin is maintained at an appropriate level for each subject. In the screening period, initial dose is 50 IU/Kg body weight three times per week. During titration, dose id titrated closely to achieve baseline Hb level 10-12g/dL. In maintenance period administer Eprex® and Epodion® equal previous stable dose in titration period. Dose is allowed to be increased or decreased during maintenance period at an appropriate level according to the condition of the subjects.
3. Only the subjects within the inclusion/exclusion criteria and achieved baselinetarget evaluation criteria should be processed to randomization and maintenance period. When the subject achieves baseline target Hb level 10- 12 g/dL in 4 weeks titration period randomization will be done in week 8, if subject fail achieves Hb 10-12 g/dL in 4 weeks titration period, titration period will be extended until week 8. Subject will be screened failure and cannot enter maintenance period if during maximum 8 week titration cannot achievetarget baseline Hb level 10-12 g/dL.
4. Safety assessment will be evaluated based on comparison incidence of adverse event between Epodion® and Eprex®. Incidence of adverse eventswill be recorded during maintenance and evaluation period.

CHAPTER I. INTRODUCTION

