2.4 Epodion®

Epodion® is an alpha rhEPO product produced by PT. Daewoong Pharmaceutical Company Indonesia. This product is used in conjunction with other clinical treatments for anemic patients due to chronic kidney disease or due to chemotherapy. Yellowish transparent Epodion® injection solution which can be injected intravenously or subcutaneously. Epodion® has four products with different EPO content, including 2000 IU, 3000 IU, 4000 IU, and 10000 IU.

At the beginning of Epodion® use, patients are given a dose of 50 units/kg of body weight three times a week which can be done intravenously or subcutaneously. If needed, the dose can be increased to 75 units/kg at 4-week intervals from the initial administration. If the increase in hemoglobin level increases by more than 2 gr/dL at the initial dose, the administration of Epodion® must be reduced to 2 times a week. Repair doses can be continued until the patient's hemoglobin level becomes 10 gr/dL. Anemia that has been overcome can be continued with a maintenance

dose of between 25 to 50 units/kg, 2 or 3 times a week. The expected hemoglobin range for treatment is 10-12 gr/dL. The initial hemoglobin level determines the treatment dose. In addition, the patient's age is also important in determining the dose. The dosage for the use of Epodion® should not exceed 200 units/kg and the frequency of administration is not more than 3 times a week. During treatment, the patient's iron levels need to be controlled. Chronic kidney failure patients who do not undergo hemodialysis, a dose of 70-150 units/kg per week is proven to maintain hematocrit levels 36-38% for more than 6 months.

Research on the effects of Epodion® on human bone marrow cell culture shows that Epodion® stimulates the formation of red blood cells and does not affect the formation of white blood cells. Animal studies using Epodion® showed in vivo efficacy in test animals. In addition, no cytotoxic effects were detected, changes in behavior, locomotor activity, circulation or breathing in test animals.

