5.1 Screening Period Criteria

Inclusion:

- a. Male or female patients who are at least 18 years old and younger than 75 years of age at the time of screening visit
- b. Patients with End-Stage Renal Failure (ESRD) who are chronically receiving hemodialysis and have anemia
- c. Patients with a mean baseline Hb concentration within Hb level ≥ 9 g/dL during the screening period
- d. Haemodialysis patients with anemia associated with Chronic Kidney Disease (CKD) currently receiving stable maintenance therapy with Epoetin at least once per week
- e. Adequate iron substitution status (serum ferritin ≥ 100 $\mu\text{g} / \text{L}$ (100 ng / mL) or saturated transferrin levels $\geq 20\%$)
- f. Patients who understand the information provided to them or their representatives and may provide written consent.

Exclusion:

- a. Contraindication with Epoetin therapy
- b. Documented active bleeding in the last 12 weeks prior to screening period
- c. Any blood transfusion within the last 2 weeks prior Screening period
- d. History of malignancy of any organ system within the last 5 years
- e. Patients with uncontrolled hypertension (in case the mean value of diastolic blood pressure as measured 4 times during the baseline observation period is 110 mmHg or more).
- f. Patients hyporesponsive epoetin treatment or had medical history of experiencing pure red blood cell forming failure after being administered with Epoetin products
- g. Known bone marrow fibrosis (osteitis fibrosa cystica)
- h. Patient with serious cardiovascular disorders: myocardial infarction, patients with congestive heart failure (NYHA class III or higher), ischemic vascular disease
- i. Patient received percutaneous coronary intervention (PCI), or coronary artery bypass grafting (CABG) during the last 6 months prior to screening

- j. Patients with ALT or AST exceeding the upper limits of the normal level by more than 5-folds
- k. Patients whose kidney transplant is expected or already planned for survival
- l. Secondary anemia to other causes different to the CKD (aplastic anemia, hemolytic anemia, sickle cell anemia, multiple myeloma, leukemia, myelodysplastic syndrome)
- m. Patients with the following diseases and who are considered unfit to enroll in the clinical study: mental system disease, mental disease, drug intoxication, epilepsy, lung infarction, cerebral infarction, positive HIV antibody, systemic lupus erythematosus, immunosuppressive condition and general infection

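### The protocol places a starting dose of 50 IU/kg three times weekly in the screening period, before eligibility is confirmed and in patients already on stable epoetin

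*Protocol*

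**What the plan says.** Two places in the protocol give the same dosing instruction. Section 4.4.6 has "Screening period initials dose 50 IU/Kg body weight three times per week". Footnote 2 to the schedule in the synopsis has "In the screening period, initial dose is 50 IU/Kg body weight three times per week". In both, the preceding sentence requires doses to be individualized, and the following one has the dose titrated to an Hb of 10-12 g/dL.

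Other parts of the protocol bear on who is treated, when, and at what dose:

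- **Who.** Inclusion d of section 5.1 admits patients "currently receiving stable maintenance therapy with Epoetin at least once per week".
- **When.** Section 4.4.1 says that "only subjects who meet all of the screening criteria will be proceeded for first phase of study which is titration period".
- **At what dose.** In titration, according to section 4.4.2, "all eligible subjects will be given Eprex® at individualized dose for 3 times a week through intravenous injection". The synopsis Method says the same in substance. The synopsis entry on dosage and administration ties the initial epoetin dose to the previous dose.
- **What is recorded.** The section on medical and medication history (numbered 4.1.3) collects the epoetin dose given in the 4 weeks before screening.
- **Product description.** Section 2.4 says: "At the beginning of Epodion® use, patients are given a dose of 50 units/kg of body weight three times a week". For maintenance it gives a "dose of between 25 to 50 units/kg, 2 or 3 times a week".

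The SAP contains no dosing instruction.

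**The concern.** The instruction puts a starting dose where the rest of the protocol has no study dosing. It also takes the figure that section 2.4 gives for the start of use and applies it to patients who are past that stage.

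A site that followed it to the letter would change a stable patient's epoetin during screening. Three things follow:

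- The change would come before anyone had confirmed that the patient qualifies.
- Inclusion c of section 5.1 rests on mean Hb during the screening period (at least 9 g/dL), so the change could alter a measurement on which eligibility depends.
- The two-weekly blood counts that guide dose adjustment are described in the synopsis Method for titration. The schedule headings show week -4 and week 0 with nothing between, so a new dose could run for four weeks without a scheduled Hb check.

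What is at stake is patient safety in the run-in and clean eligibility decisions.

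**Working it through.** The plan gives no figure to reproduce here. The check is a comparison of texts, followed by simple dose arithmetic.

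**Step 1: the texts side by side**

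| Question | Section 4.4.6 and schedule footnote 2 | Elsewhere in the protocol |
|---|---|---|
| When does dosing start? | Screening period | Titration, the first study phase (synopsis Method, 4.4.1, 4.4.2) |
| Who is dosed? | Not stated; eligibility is still being checked | Subjects who have met all screening criteria (4.4.1, 4.4.2) |
| At what dose? | 50 IU/kg three times weekly, no alternative offered | An individual dose (synopsis Method, 4.4.2); the previous dose (synopsis dosage entry, natural reading) |
| For which patients is that dose meant? | All | Those beginning use (2.4); entrants are already maintained (5.1 d) |

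The synopsis dosage entry could be read another way. Section 6.2 uses the idea of a previous dose for the titration dose carried into maintenance, and the synopsis may mean the same. The conflict with sections 4.4.1, 4.4.2 and 5.1 d does not depend on that entry.

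Section 6.2 also says that product is given from enrolment. It does not say whether enrolment precedes or follows screening, so it does not settle the timing.

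**Step 2: the weekly dose**

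Weekly dose = dose per kg × administrations per week.

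- Written starting dose: 50 × 3 = 150 IU/kg per week.
- Section 2.4 maintenance range, low end: 25 × 2 = 50 IU/kg per week.
- Section 2.4 maintenance range, high end: 50 × 3 = 150 IU/kg per week.

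**Step 3: the change for a stable patient**

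Ratio = written starting dose / previous weekly dose.

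- Previous dose 150: 150/150 = 1, no change.
- Previous dose 50: 150/50 = 3, a threefold increase.

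The written dose is therefore at the top of the maintenance range. Eligibility sets no range for the previous dose, so these ratios rest on an assumption: that the Epodion maintenance range describes what entrants were receiving, whatever their epoetin product.

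For a patient above 150 IU/kg per week the change would be downward. Section 2.4 says the dose "should not exceed 200 units/kg and the frequency of administration is not more than 3 times a week", which gives 200 × 3 = 600 IU/kg per week and a ratio of 150/600 = 0.25. That is an outer bound, not an expected case.

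**Step 4: what cannot be computed**

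The documents give no distribution of previous doses. The number of patients whose dose would change, and by how much, is unknown.

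**The case against.** The strongest reply is that this is a slip in a period label. The disputed sentence names no product and calls the dose initial. It stands between a requirement to individualize and an instruction to titrate. A per-kg starting point followed by titration is an ordinary form of individual dosing. Three other places already give the right timing. The Eprex row of the schedule has lost its cell positions, and the study-flow figure is not shown, so the schedule itself may have settled the matter.

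Much of this stands. The slip is plausible, and it would be wrong to read the sentence as imposing a rigid dose. But nothing readable says that it is a slip, and the instruction appears twice, once in the section that governs dosing. A site cannot tell which sentence decides a stable patient's first dose. If the slip is accepted, the timing conflict goes, but a single starting figure for already maintained patients would still need reconciling with the previous-dose rule.

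The reply is also right about consequences. A reader might infer that the starting dose leads to exclusion under criterion b of section 5.2, which removes subjects whose dose changes by 20% or more. That criterion counts only changes within the baseline evaluation period, which follows 4 to 8 weeks of titration, so a screening dose cannot itself trigger it. Screen failure under schedule footnote 3 requires Hb to miss 10-12 g/dL after up to 8 weeks of titration. Entry needs only Hb of at least 9 g/dL, so some dose adjustment is expected in the run-in anyway. A reader might also turn to section 2.4's subcutaneous bioavailability to size the problem. Those figures concern conversion between routes and do not measure this contradiction.

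**Conclusion.** The protocol is wrong as written: it contains a contradictory operative dosing rule. Severity is minor. Section 4.4.6 and schedule footnote 2 place 150 IU/kg per week in screening. Sections 4.4.1 and 4.4.2 and the synopsis Method start Eprex later, in eligible subjects, at an individual dose.

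If previous doses lay within section 2.4's maintenance range, following the rule literally means a 1- to 3-fold upward change. That range is an assumption, and the number of patients affected is unknown.

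The effect is confined to run-in safety and eligibility. A reader might infer that the equivalence comparison is biased, but the documents do not support that. Section 4.4.2 puts all subjects on Eprex in titration, before randomisation. Baseline is measured after titration, and the dose sentence does not distinguish the arms. The endpoint, the analysis and the sample size are untouched.

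**What to change.** 1. Delete the screening-period dose from section 4.4.6 and from schedule footnote 2.
2. State that each patient's usual epoetin continues unchanged during screening.
3. State in the synopsis dosage entry, schedule footnote 2 and section 4.4.6 that Eprex starts at titration week 0, after eligibility is confirmed, at an individual dose. The reference is the previous dose already recorded under the medication-history section. The investigator adjusts it where the earlier route or frequency differs from intravenous dosing three times weekly.

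An equal weekly dose should not be mandatory, because inclusion d sets no route and asks only for at least one administration a week.

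The cost is protocol wording in three places, plus a clinical judgement for patients coming from another route or frequency. No new data, visits or subjects are needed.
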